8.2.4.2. Axitinib Dose Reduction for Hemoptysis

Bleeding from the lungs as evidenced by hemoptysis will be graded according to the site specific hemorrhage category of CTCAE v4.03.

Treatment with Axitinib will be discontinued for hemoptysis of $>\frac{1}{2}$ tsp of bright red blood per day. In addition, a radiologic assessment (e.g., chest x-ray) should be considered for patients who have hemoptysis $>\frac{1}{2}$ tsp of bright red blood per day. If the hemoptysis resolves to baseline within 1 week and there is no evidence of disease cavitation, treatment with Axitinib may continue at the current dose level. Patients who experience hemoptysis without resolution to baseline within 1 week, or with evidence of disease cavitation should discontinue from treatment with Axitinib.

8.2.4.3. Axitinib Dose Reduction for Proteinuria

At documentation of >1+ proteinuria by dipstick, patients should have a 24-hour urine collection for total protein. Axitinib dosing may continue while waiting for test results.

If ≤ 2 g proteinuria/24 hours is reported, treatment with Axitinib may continue without dose reduction.

If >2 g proteinuria/24 hours is reported, treatment with Axitinib should be interrupted. A twenty-four hour urine collection for total protein and creatinine clearance should be performed weekly until results show \leq 2 g proteinuria/24 hours, at which time treatment with Axitinib may be restarted at one lower dose level. Patients, once restarted on Axitinib, will have every-2-weeks monitoring for proteinuria by semiquantitative testing (e.g., dipstick) as long as the proteinuria reading is higher than 1+. The 24-hour urine collection to monitor the degree of proteinuria should be repeated every 4 weeks until it has decreased to <500 mg/24 hours. If recurrent >2 g proteinuria/24 hours is reported, treatment with Axitinib should be interrupted again. Twenty-four hour urine collection for total protein and creatinine clearance should be performed every 2 weeks until results show \leq 2 g proteinuria/24 hours, at which time treatment with Axitinib may be restarted at one lower dose level. If a patient requires dose reduction below 2 mg BID, stop trial participation.

8.2.4.4. Axitinib Dose Interruption for Surgery or Surgical Procedures

If surgery is required, treatment with Axitinib must be interrupted at least 24 hours before the procedure and the patient's blood pressure should be monitored closely for hypotension. Patients may resume Axitinib seven days after minor surgery and 2-3 weeks after major surgery, assuming wound has completely healed and no wound healing complications, at the discretion of the prescribing physician.

8.2.4.5. Thyroid Function Tests

Patients receiving Axitinib should be monitored for signs and symptoms of hypothyroidism, such as fatigue, deepening of voice, cold intolerance, constipation, anorexia, periorbital edema, myxedema, or changes in skin or hair. Hypothyroidism should be treated per standard medical practice to maintain euthyroid state. Dose reduction or interruption should not be made for thyroid abnormalities alone.

8.3 Treatment Beyond Disease Progression

As described in Section 1.2, traditional imaging response criteria may not fully capture response to tyrosine-kinase inhibitors, particularly anti-angiogenic agents. Although the Choi Criteria have been proposed for evaluating response to tyrosine kinase inhibitors, these response criteria

likely still do not fully capture patients who may derive clinical benefit despite radiologic evidence of PD.

Subjects will be permitted to continue on Axitinib treatment beyond initial Choi defined PD as long as they meet the following criteria:

- Investigator-assessed clinical benefit and do not have rapid disease progression
- Tolerance of study drug
- Stable performance status
- Treatment beyond progression will not delay an imminent intervention to prevent serious complications of disease progression (i.e. CNS metastases)
- Subject provides written informed consent prior to receiving any additional Axitinib treatment, using an informed consent describing any reasonably foreseeable risk or discomforts, or other alternative treatment options.

The assessment of clinical benefit should take into account whether the subject is clinically deteriorating and unlikely to receive further benefit from continued treatment.

All decisions to continue treatment beyond initial progression must be documented in the study records. Subjects will be re-consented with an informed consent describing any reasonably foreseeable risks or discomforts.

Subjects should discontinue study therapy upon further evidence of further progression, defined as an additional 10% or greater increase in tumor burden volume from time of initial progression (including all target lesions and new measurable lesions).

New lesions are considered measurable at the time of initial progression if the longest diameter is at least 10 mm (except for pathological lymph nodes, which must have a short axis of at least 15 mm). Any new lesion considered non-measurable at the time of initial progression may become measurable and therefore included in the tumor burden measurement if the longest diameter increases to at least 10 mm (except for pathological lymph nodes, which must have an increase in short axis to at least 15 mm).

For statistical analysis that include the investigator-assessed progression date, subjects who continue treatment beyond investigator-assessed, Choi Response defined progression will be considered to have investigator-assessed progressive disease at the time of the initial progression event.

8.4. Drug Storage and Drug Accountability

A co-investigator or an approved representative (e.g., research pharmacists) will ensure that all trial drugs are stored in a secure area, under recommended storage conditions and in accordance with applicable regulatory requirements.

The research pharmacy will assist with management of drug storage and accountability. Drug accountability forms will be used to maintain accurate records of receipt, dispensing and return

of trial medication. Any drug that is not dispensed at the end of the trial or any returned drug supplies should be returned to Pfizer Inc., or disposed of in accordance with instructions received in writing from Pfizer, Inc.

8.5. Concomitant Medication(s)

In vitro studies with human liver microenzymes and recombinant CYP450 enzymes indicated that Axitinib metabolism was primarily mediated by the drug-metabolizing enzyme CYP3A, and to a lesser extent by CYP1A2. Additionally, the drug also undergoes N-glucuronidation in liver microsomes of some species. Clinically, there is likelihood that Axitinib plasma concentrations may be increased in the presence of co-administered potent inhibitors of the CYP3A and glucuronosyl transferase enzymes. The potential exists for drug-drug interactions with strong CYP3A4/5 inhibitors and inducers.

Axitinib metabolism may be induced in patients taking strong CYP3A4/5 inducers and inhibitors as these may alter Axitinib plasma concentrations.

The following potent CYP3A4/5 strong inhibitors and CYP3A4/5 strong inducers are prohibited:

CYP3A4/5 INHIBITORS (Strong)

Atazanavir Boceprevir Coniveptan Clarithromycin Grapefruit and grapefruit juice Indinavir Itraconazole Ketoconazole Nefazodone Nelfinavir Posaconazole Ritonavir Saquinavir Telaprevir Telithromycin Voriconazole

CYP3A4/5 INDUCERS (Strong)

Carbamazepine Dexamethasone Fosphenytoin Phenytoin Phenobarbital Rifampin Rifapentin Rifabutin St. John's Wort

Other CYP3A4/5 inhibitors and inducers are allowed per investigator's discretion.

Since CYP1A2 is also known to be induced in chronic smokers, there is likelihood that Axitinib plasma concentrations may be reduced in these individuals. Based on preclinical and extensive clinical experience, clinically significant drug interactions are unlikely.

8.6. Rescue Therapy

No mechanistically specific antagonists for Axitinib are available and standard supportive measures should be used in the case of excessive pharmacological effects or adverse reaction.

9. RESPONSE CRITERIA

The Choi Criteria will be used to assess tumor response to therapy. Interpretation will be performed by centralized UMCC Tumor Response and Assessment Core (TRAC). If density measurements are not available and cannot be accurately measured by photography or imaging, response can be dictated by measurement alone (i.e.for cutaneous squamous cell carcinomas that are not visualized on CT scan but are measurable on physical exam only). Non-target lesions are also permissible in which case overall assessment would be limited to complete response, stable disease, and progressive disease.

Complete Response:

- Disappearance of all lesions
- No new lesions

Partial Response:

- A decrease in size¹ of $\ge 10\%$ or a decrease in tumor density (HU) $\ge 15\%$ on CT
- No new lesions
- No obvious progression of non-measurable disease

Stable Disease

- Does not meet the criteria for CR, PR, or PD
- No symptomatic deterioration attributed to tumor progression

Progressive Disease

- An increase in tumor size of \geq 10% and dose not meet criteria of PR by tumor density (HU) on CT
- New lesions
- New intratumoral nodules or increase in the size of the existing intratumoral nodules
- ¹⁻ The sum of longest diameters of target lesions as defined in RECIST

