3.2 Secondary objectives

- 1. To determine the overall survival of patients treated with Axitinib
- 2. To determine the progression free survival of patients treated with Axitinib
- 3. To determine the disease control rate at 16 weeks and response rate as defined by Choi Criteria
- 4. To determine the duration of response (as defined by Choi Criteria) of patients treated with Axitinib
- 5. To assess the toxicities associated with the treatment of Axitinib of patients treated with Axitinib

4. STUDY DESIGN:

This study will be a prospective, single-institution, single-arm phase II study of Axitinib in patients with unresectable recurrent and metastatic head and neck squamous cell carcinoma with ECOG performance status 0-2, for recurrent or metastatic head and neck cancer. The subjects will be started on treatment with 5 mg of Axitinib twice a day continuously, with subsequent dose escalation to 7 mg and then 10 mg twice a day in the absence of grade 2 or worse toxicities. This will be followed by clinical and/or radiologic response assessment after 8 weeks and subsequently every 2 months until disease progression (defined per Choi criteria, or obvious progression on clinical or laryngoscopic/endoscopic exam) or intolerable toxicity (defined as below). Patients with confirmed progressive disease who, in the investigator's opinion, continue to receive benefit from Axitinib treatment and who meet the criteria for treatment may continue to receive treatment as described in Section 8.3. Axitinib should be discontinued if there is further evidence of progression defined as an additional 10% or greater increase in tumor burden volume from time of initial progression (including all target lesions and new measurable lesions).

During treatment on this protocol, all patients will be evaluated for safety as detailed below.

5. STUDY POPULATION:

5.1. Stage:

Unresectable, recurrent or metastatic squamous cell carcinoma of head and neck.

5.2. Inclusion Criteria:

1. Histologically documented squamous cell head and neck cancer with or without metastases, not amenable to curative treatment; or the patient has documented refusal of curative treatment.

2. Presence of measurable disease by CT scan or

a. for cutaneous squamous cell carcinoma not present on CT imaging but present on physical exam with lesion(s) greater than >/= 10mm

b. patients with non-target lesions are permissible per PI discretion

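### The progressive-disease list has no criterion for growth of existing non-target or non-measurable disease, so some progressing patients can be rated stable, or left without a rating, in the disease control and PFS endpoints

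*Combined protocol and SAP*

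**What the plan says.** Section 5.2 item 2 requires measurable disease, but item 2b adds that "patients with non-target lesions are permissible per PI discretion". No cap is set. For these patients Section 9 removes partial response (PR) and keeps the other three categories: "Non-target lesions are also permissible in which case overall assessment would be limited to complete response, stable disease, and progressive disease".

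Section 9, repeated in Table 5 of Section 1.2, gives three routes to PD:

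- growth in tumor size of at least 10% that "dose not meet criteria of PR by tumor density (HU) on CT";
- the appearance of any new lesion;
- "New intratumoral nodules or increase in the size of the existing intratumoral nodules".

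The footnote on size reads "The sum of longest diameters of target lesions as defined in RECIST". Its marker stands on the PR bullet and not on the PD bullet. Progression of non-measurable disease appears once, as a condition for PR: "No obvious progression of non-measurable disease". SD is defined by exclusion, "Does not meet the criteria for CR, PR, or PD", with one further condition: "No symptomatic deterioration attributed to tumor progression".

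Two other places bear on this. Section 4 ends treatment at progression by the Choi criteria or at obvious progression on clinical or endoscopic examination. Section 13.4 bases progression in the analysis on the Choi criteria and does not repeat the examination route. Section 14.3 counts SD as disease control at 16 weeks.

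**The concern.** The plan admits patients whose disease lies partly or wholly outside the target lesions and says they can be rated PD, but gives no rule for growth of that disease. Because SD collects whatever is left over, the missing rule does not produce a neutral result. Where it acts, it turns a progression into disease control and pushes the PFS event later. Both errors favour the drug, and a single-arm trial has no control arm to share them.

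The gap also reaches patients who do have target lesions. Obvious progression of their non-measurable disease blocks PR but does not trigger PD.

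Disease control at 16 weeks and PFS are secondary objectives (Section 3.2). Section 2.2 also hypothesises that the Choi criteria assess response more accurately, and an incomplete PD list weakens any test of that.

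**Working it through.** **Step 1. Take three patients through the Section 9 lists.** None has a new lesion or a new or growing intratumoral nodule.

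| Patient | CR | PR | PD | SD |
|---|---|---|---|---|
| A: target sum unchanged; existing non-measurable disease clearly progressing on imaging; no symptoms | No, lesions remain | No, barred by the non-measurable condition even if density falls | No bullet met | Met, by default |
| B: only non-target lesions, growing on imaging; no symptoms | No | Not available | No target sum to apply 10% to; no other bullet met | Met, by default |
| C: as A or B, with symptomatic deterioration from tumor progression | No | No | No bullet met | Barred by the second SD condition |

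A and B are rated stable while progressing. C has no category at all. The Section 4 examination route could capture A, B or C if progression is obvious on examination. It cannot capture progression visible only on imaging, and Section 13.4 does not say whether it counts for PFS.

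**Step 2. Confirm that the primary analysis is untouched.** Inputs from Section 13.2: 37 patients, 50% against 70% alive at 6 months, one-sided 5%, power 80%. Normal approximation:

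n = [(1.645 × √0.25 + 0.842 × √0.21) / 0.20]² = 36.5, rounded up to 37.

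By the exact binomial, declaring success at 24 or more of 37 alive gives a type I error of 0.0494 and power of 0.807. The plan's figure is reproduced. No response category enters it.

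**Step 3. Size the effect on disease control.** Each patient moved wrongly from PD to SD adds 1/37 = 2.7 percentage points. The denominator of 37 is itself an assumption, since Section 13.4 uses evaluable patients. The number affected is not in the documents; I take 1 to 4:

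- 1 patient: 1/37 = 2.7 points
- 2 patients: 2/37 = 5.4 points
- 4 patients: 4/37 = 10.8 points

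To illustrate, assume a true rate of 27/37 (exact 95% intervals):

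| Misclassified | Observed rate | 95% interval |
|---|---|---|
| 0 | 27/37 = 73.0% | 55.9% to 86.2% |
| 2 | 29/37 = 78.4% | 61.8% to 90.2% |
| 4 | 31/37 = 83.8% | 68.0% to 93.8% |

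**Step 4. PFS.** In the binomial PFS rates at 2, 4 and 6 months, each missed progression adds at most the same 2.7 points. On the Kaplan-Meier curve the event moves to a later assessment. Scans are nominally 8 weeks apart with a window of 2 weeks either way (Section 7.1), but no minimum delay follows from the documents: another PD criterion, death, or an examination at a monthly visit may intervene sooner.

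**The case against.** A reader might infer that every patient with only non-target disease is scored stable while growing, or that growth in such a patient can never be PD. The documents do not support that, for four reasons.

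- The target-lesion footnote is attached to the PR bullet. The PD bullet speaks of tumor size without the marker, so a central reader is not plainly barred from applying it more widely. This stands as an ambiguity. It does not supply a rule: a 10% threshold cannot be applied to disease that is not measurable, and readers would have to improvise.
- Symptomatic deterioration excludes SD. This stands, and it takes those patients out of the inflated count. It leaves them unclassified, because no PD bullet picks them up.
- Section 4 recognises obvious progression on clinical or endoscopic examination, and response is assessed clinically at each visit. This stands and narrows the group to growth seen only on imaging. The Section 13.4 sentence may be meant only as a contrast with the RECIST-based predecessor trial, not as an exclusion of the examination route. That has to be stated.
- New lesions and growing nodules are PD in any patient. True, but neither covers enlargement of existing disease.

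It would also go too far to say that each missed progression delays PFS by at least one scan interval, or to attach a firm number to the inflation. Nor does the gap necessarily prolong treatment, since Section 8.3 already allows treatment past Choi progression on the investigator's judgement. Finally, the affected endpoints are secondary and carry no hypothesis test.

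**Conclusion.** The concern holds in a limited form. As written, the response rule rates asymptomatic, imaging-only growth of existing non-target or non-measurable disease as SD, and gives no category to a patient whose symptoms rule out SD but who meets no PD bullet. Where this occurs, 16-week disease control and PFS are biased in the drug's favour. The size cannot be derived. On the assumption of 1 to 4 affected patients in a denominator of 37, disease control is overstated by 2.7 to 10.8 percentage points. The primary endpoint, sample size, type I error and power do not change. The change should be made because it is cheap and the bias runs one way, but the trial's main conclusion does not depend on it.

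**What to change.** For the disease control and PFS endpoint definitions, add a fourth item to the PD list in Section 9 and Table 5: unequivocal progression of existing non-target or non-measurable disease, as read by TRAC. State which PD criteria apply to patients without target lesions.

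Reconcile Sections 4, 9 and 13.4 on whether obvious clinical or endoscopic progression is a PFS event.

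Section 4 also ties treatment duration to progression, and the further-progression rule in Sections 4, 7.1 and 8.3 counts target lesions and new measurable lesions only. These treatment passages must therefore be reconciled with the revised definition. That is for the investigators to settle; no stopping rule is proposed here.

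The cost is a short amendment and a reading instruction for TRAC, with no added scans or patients. The list will no longer be exactly the one the protocol presents as the Choi criteria, and reports should say so. Reported disease control and PFS may be slightly less favourable.

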10. CRITERIA FOR DISCONTINUATION OF TREATMENT

- 1. Unacceptable toxicity.
- 2. Intercurrent illness, which prevents further administration of treatment.
- 3. Patient preference.
- 4. Confirmed PD and Investigator determination that the patient is no longer benefiting from treatment with Axitinib (per section 8.3)
- 5. Treatment delays due to drug-related toxicity > 2 weeks.
- 6. Non-compliance with treatment.

7. If the disease becomes amenable to resection or (chemo) radiation with curative intent as a result of Axitinib treatment, Axitinib will be stopped, and the alternative treatment instituted that would offer the best chance of cure for the patient. Such patients will be included in safety and efficacy analysis.

11. SAFETY ASSESSMENTS

The safety of Axitinib should be evaluated using the standard clinical practice, with special attention paid to hypertension, proteinuria, thrombosis, hemoptysis, bleeding risk, and concomitant medications. Patients receiving Axitinib should be monitored for signs and symptoms of hypothyroidism, such as fatigue, deepening of voice, cold intolerance, constipation, anorexia, periorbital edema, myxedema, or changes in skin or hair. Hypothyroidism should be treated per standard medical practice to maintain euthyroid state.

12. ADVERSE EVENT REPORTING

12.1. Adverse Events

All observed or volunteered adverse events regardless of suspected causal relationship to Axitinib will be reported as described in the following sections.

For all adverse events the investigator must pursue and obtain information adequate both to determine the outcome of the adverse event and to assess whether it meets the criteria for classification as a serious adverse event requiring immediate notification to Pfizer, Inc. or its designated representative. For all adverse events sufficient information should be obtained by the investigator to determine the causality of the adverse event. The investigator is required to assess causality. For adverse events with a causal relationship to Axitinib, follow-up by the investigator is required until the event or its sequelae resolve or stabilize at a level acceptable to the investigator, and Pfizer, Inc. concurs with that assessment.

12.2. Reporting Period

Adverse events reporting, including suspected, unexpected serious adverse reactions, will be carried out in accordance with applicable local regulations. For serious adverse events, the reporting period to Pfizer, Inc. or its designated representative begins from the time that the subject has taken at least one dose of trial treatment through the last subject visit. Any serious adverse event occurring any time after the reporting period must be promptly reported if a causal relationship to Axitinib is suspected.

Adverse events should be recorded on the CRF from the time the subject has taken at least one dose of trial treatment through last subject visit.

If a patient begins a new anticancer therapy, the adverse event reporting period for non-serious adverse events ends at the time the new treatment is started. Death must be reported if it occurs

during the serious adverse event reporting period after the last dose of investigational product, irrespective of any intervening treatment.

